Participants who are naïve to anti-PD-1, anti-PD-L1, and anti-CTLA-4 treatment will be enrolled in Track 1, and they will be randomized to nivolumab in combination with ipilimumab or to one of the FRACTION-RCC study treatment combinations. Randomization will be stratified by whether or not the participant has had prior TKI treatment. These participants will receive their assigned study treatment in Track 1 until completion of the Treatment Phase.

Participants who have received prior anti-PD-1, anti-PD-L1, or anti-CTLA-4 treatment will be enrolled in Track 2 and randomized to nivolumab in combination with ipilimumab or to one of the FRACTION-RCC study treatment combinations. In addition, participants with PD who were treated in Track 1 or 2 and continue to fulfill all entry criteria may be enrolled in Track 2 and re-randomized to a new combination other than that previously received, if applicable. These participants will receive their assigned study treatment in Track 2 until completion of the Treatment Phase. The number of participants who initially enroll in Track 2 and those who enroll in Track 2 after treatment on Tracks 1 or 2 is described in [Section 10.1](#).

- **Participants with CR, PR, or SD** at the end of 2 years on Track 1 or 2 Treatment Phase will:
 - Enter study safety follow-up (FU) and complete FU1, FU2, and FU3 visits
- **Participants with PD** during the Track 1 or 2 Treatment Phase will:
 - Enter study follow-up (Not applicable per Protocol Amendment 07)
 - Enter (or re-enter) Track 2, if eligible and if a new study treatment combination is available, and be randomized to a new combination. (Re-randomization is no longer applicable per Protocol Amendment 07)
 - Continue treatment beyond progression if criteria in [Section 7.4.2](#) are met. (Not applicable per Protocol Amendment 07)
 - Enter safety follow-up and complete FU1, FU2, and FU3 visits.
- **Participants with CR, PR, or SD who enter study follow-up and subsequently progress** will:
 - Enter (or re-enter) Track 2, if eligible and if a new study treatment combination is available, and be randomized to a new combination. (Re-randomization is no longer applicable per Protocol Amendment 07)
 - Enter safety follow-up and complete FU1, FU2, and FU3 visits

Figure 5.1.1-1: Tracks 1 and 2 Study Design Schematic

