5.1.3.1 Screening

Prior to screening for the protocol, investigative sites are required to determine if a participant has previously received anti-PD-1, anti-PD-L1, anti-CTLA-4, or TKI treatment through their Institutional database, participant medical history, or Institutional prescreening process. Once determined, treatment experience is considered source data for this FRACTION-RCC study. The participant must be provided with the FRACTION-RCC study Institutional Review Board (IRB)-approved written consent. Once the consent is signed, the participant is then considered to have entered screening. The treatment status must be entered into the enrollment management system, and participants will be required to submit a fresh tumor biopsy to the central laboratory. An adequate baseline tumor biopsy (as determined by a central laboratory pathologist or a local pathologist) must be obtained prior to randomization.

The Screening Phase for each Track will last for up to 28 days. Participants will be enrolled using Interactive Response Technology (IRT).

If a participant surpasses the 28-day window during the Screening Phase due to a study-related procedure (eg, scheduling of a tumor biopsy or waiting time for a study-related laboratory value), the participant must be re-consented but does not need to be assigned a new participant identification number. To reduce any undue burden of procedure in this participant population in this situation, the amount of repeat procedures from the initial screening will be minimized while maintaining safety and eligibility under the discretion of the BMS Medical Monitor (or designee) and investigator.

Enrollment in all study treatment arms in each Track will be competitive.

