7.2 Method of Treatment Assignment

This is an open-label study. All participants will be centrally randomized using an IRT. Before the study is initiated, each user will receive log-in information and directions on how to access the IRT.

Specific study treatments are listed in each FRACTION- RCC Sub-Protocol. Study treatment will be dispensed at the study visits as listed in the On-treatment Procedural Outline(s) in each FRACTION-RCC Sub-Protocol.

All participants must be assigned a patient identification number (PID) upon providing a signed IRB/IEC-approved written informed consent. During the screening visit, the investigative site will utilize the IRT for enrollment and receive a 5-digit PID designated by BMS that will be unique across all sites. Enrolled participants, including those not dosed, will be assigned sequential PIDs starting with 00001 (eg, 00001, 00002, 00003...00010). The PID will ultimately be composed of the site number and participant number. For example, the first participant screened (eg, enrolled) at Site Number 1 will have a PID of 0001-00001. The following information is required for enrollment:

- Date of obtaining informed consent
- Date of birth
- Gender at birth
- Anti-PD-1, anti-PD-L1, or anti-CTLA-4 treatment experience (see [Section 5.1.3.1](#))

Once enrolled in the IRT, participants who meet all eligibility criteria will be ready to be randomized through the IRT. The following information is required for randomization:

- Participant number
- Date of birth

Randomization participant schedules will be generated and maintained by the IRT vendor. At the conclusion of the trials, BMS will receive copies of all generated participant schedules from the vendor. Because of the nature of the study design, limited early access to the randomization information will be granted to the study team to facilitate early analyses for internal decision making (early termination of study treatment arm, etc).

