Each participant who is randomized will be assigned a unique randomization number. This is not the primary identifier for the participant but used for the randomization schedule. The primary identifier will be the PID described above, for use on the case report form (CRF) and source documents. A participant being re-randomized in Track 2 will be assigned a different randomization number but will retain the same PID. Randomization numbers will be assigned using a Central Randomization System in the order in which participants qualify for study treatment, not in the order of study enrollment. Randomization ratios within each Track will be specified in each FRACTION-RCC Sub-Protocol. If, within a given Track, study treatment arms from more than 1 FRACTION-RCC Sub-Protocol within the FRACTION-RCC Master Protocol are simultaneously open to enrollment, then a new participant could be assigned to any of the open study treatment arms. In Track 1, randomization of participants will be stratified by whether or not the participant has had prior TKI treatment. In Track 1, participants will be randomized to newly added study treatment arms/study treatments (through FRACTION-RCC Sub-Protocols) in a ratio as specified in each new FRACTION-RCC Sub-Protocol. New randomization schedules for new FRACTION-RCC Sub-Protocols will be generated. If accrual for current FRACTION-RCC Sub-Protocols is still ongoing, participants will be allocated to the existing randomization schedule or new randomization schedule based on a prespecified allocation ratio. Details of allocation ratio will be specified in the new FRACTION-RCC Sub-Protocol. In Track 2, participants will be randomized to existing study treatment arm/study treatments and newly added study arm/study treatments with equal probability.

Prespecified study treatment arm caps (according to Simon 2-stage [optimal] design) will be utilized to control the accrual for each combination study treatment arm under different Tracks (Tracks 1 and 2). The cap for the nivolumab in combination with ipilimumab control arm under Track 1 will be set equal to the largest cap among its corresponding experimental arms. In the event that 1 or more participants go off study without being evaluable for response (ie, with no postbaseline tumor measurements and no evidence of clinical progression or death due to disease

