10 STATISTICAL CONSIDERATIONS

Additional statistical considerations may be provided in each subprotocol. Please refer to the specific sub-protocol for guidance.

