10.3 Statistical Analyses

The statistical analysis plan will be developed and finalized before database lock. Below is a summary of planned statistical analyses of the primary and secondary endpoints.

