Abbreviations: DOR = duration of response; ORR = overall response rate; OS = overall survival; PFSR = progression free survival rate.

Track 1 - Anti-PD-1, Anti-PD-L1, and Anti-CTLA-4 Treatment-naïve Participants

The following additional analyses will be performed for Track 1 anti-PD-1, anti-PD-L1, and anti-CTLA-4 treatment-naïve participants at the end of Stage 2. These efficacy analyses will be performed when the study treatment arms have been fully enrolled and followed up for at least 6 months. A descriptive odds ratio and estimate of the difference in ORRs, along with corresponding 2-sided 95% CIs, will be provided to evaluate differences between the 2 randomized study treatment arms (FRACTION- RCC study treatment combination arm and nivolumab in combination with ipilimumab control arm). Additionally, for each study treatment arm, the ORR and corresponding 95% CIs will be calculated using Clopper-Pearson method. A descriptive hazard ratio and corresponding 2-sided 95% CI of PFS and OS will be estimated in a Cox proportional hazards model using study treatment as a single covariate to evaluate difference between the 2 study treatment arms (experimental and control arms). The PFS and OS curves for each study treatment arm will be estimated. Two-sided 95% CIs for median PFS and OS will be computed. PFSR at 24 weeks and survival rates at certain time points (eg, 2 years) will be estimated. Associated 2-sided 95% CIs will be calculated.

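### Track 1 is randomised within prior-TKI strata, but the planned Cox model is unstratified and no strata are named for the odds ratio or ORR difference

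*Combined protocol and SAP*

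**What the plan says.** Section 5.1.1 states for Track 1: "Randomization will be stratified by whether or not the participant has had prior TKI treatment". Section 7.2 repeats it: "In Track 1, randomization of participants will be stratified by whether or not the participant has had prior TKI treatment".

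The Track 1 part of section 10.3.1 sets out the comparison of each combination with the nivolumab plus ipilimumab control at the end of Stage 2. For response: "A descriptive odds ratio and estimate of the difference in ORRs, along with corresponding 2-sided 95% CIs, will be provided to evaluate differences". It gives no between-arm method and no strata. For PFS and OS, a descriptive hazard ratio with a 95% CI is to be "estimated in a Cox proportional hazards model using study treatment as a single covariate to evaluate difference between the 2 study treatment arms". Prior TKI does not appear anywhere in section 10 as a stratum, covariate or subgroup.

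Two statements leave room for later detail. Section 10.3 says that the SAP will be finalised before database lock, and adds: "Below is a summary of planned statistical analyses of the primary and secondary endpoints". Section 10 opens with: "Additional statistical considerations may be provided in each subprotocol".

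**The concern.** When randomisation is stratified, the usual practice is to carry the stratum into the between-arm analysis. If the stratum is prognostic and the analysis ignores it, the hazard ratio and odds ratio sit somewhat closer to 1 than the effect within strata, and the intervals are slightly conservative.

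The contrast has a purpose. The primary objective in section 4 is efficacy relative to nivolumab plus ipilimumab where applicable, and section 10.1.1 lists the relative performance of other arms among the data reviewed before an arm is stopped or continued, although it does not tie that review to this hazard ratio. The Cox wording is an affirmative specification, so an SAP author who follows it would probably fit the unstratified model. For ORR the text is silent, which is a gap and not a wrong rule.

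**Working it through.** **Inputs from the documents.** Up to 63 per Track 1 combination arm (section 5.2, Table 10.1-1); control cap equal to the largest experimental cap (section 7.2), so 63 against 63 is assumed; at least 6 months of follow-up (section 10.3.1); control median PFS 11.6 months and ORR 41.6% for nivolumab plus ipilimumab in untreated intermediate- or poor-risk patients (section 3.2.1); ORR about 25% for nivolumab alone after anti-angiogenic therapy (sections 3.2.1 and 10.1).

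**Assumptions not in the documents.** Half the participants TKI-naive and strata balanced between arms; the PFS and ORR figures above borrowed as stratum-level control values; exponential PFS; censoring uniform from 6 to 24 months; hazard ratio between strata φ from 1.0 to 2.5.

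**1. The plan's own figures.** Exact two-stage binomial calculation for the Track 1 rule (8/24, 24/63) gives a 72.5% chance of stopping at Stage 1 and a 4.97% false positive rate at 30% ORR, and 90.3% power at 50%. The plan states 73%, 5% and 90%. These are single-arm response counts, so stratifying the between-arm contrast changes none of them. The plan gives no event count or power for that contrast.

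**2. Hazard ratio.** Hazard = (ln 2 / 11.6) × θ^x × φ^s, with x = 1 for the experimental arm, s = 1 for TKI-experienced and θ the within-stratum hazard ratio. There were 6,000 trials per setting, with 62 to 90 events on average. Results for θ = 0.60, unstratified / stratified Cox:

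| φ | Average HR | 95% CI excludes 1 | RMSE of log HR |
|---|---|---|---|
| 1.0 | 0.601 / 0.601 | 49.5% / 48.6% | 0.259 / 0.260 |
| 1.5 | 0.606 / 0.600 | 53.5% / 54.6% | 0.245 / 0.249 |
| 2.0 | 0.612 / 0.596 | 56.0% / 59.6% | 0.227 / 0.238 |
| 2.5 | 0.628 / 0.599 | 53.9% / 60.8% | 0.221 / 0.235 |

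- The largest shift is 0.628 − 0.599 = 0.029.
- Coverage of θ at φ = 1.5, 2.0 and 2.5 is 95.1%, 95.9% and 95.9% unstratified, against 94.9%, 95.2% and 95.2% stratified.
- At θ = 0.75 and the same φ: 0.753, 0.759 and 0.768 unstratified; 0.749, 0.747 and 0.746 stratified.
- At θ = 1.0 both methods average 0.995 to 1.000. The CI excludes 1 in 3.6 to 4.6% of trials unstratified and 4.6 to 5.3% stratified.
- With 30% TKI-naive, θ = 0.60 and φ = 2.0: 0.614 against 0.601, and the CI excludes 1 in 58.2% against 61.8%.
- A separate simulation of 3,000 trials at θ = 0.60, φ = 2.0 gave 0.617 against 0.595, and 54.9% against 60.3%.

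**3. Odds ratio and ORR difference.** Take control rates of 41.6% (TKI-naive) and 25% (TKI-experienced) and a within-stratum OR of 2.0.

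- Experimental rates: odds 0.416/0.584 × 2 = 1.425, so 58.8%; odds 0.25/0.75 × 2 = 0.667, so 40.0%.
- Averages: control (41.6 + 25)/2 = 33.3%; experimental (58.8 + 40.0)/2 = 49.4%. The difference is 16.1 points by either method.
- Crude OR: (0.494/0.506)/(0.333/0.667) = 1.95, against 2.0 within strata.
- SE of the difference, unstratified: √[(0.333×0.667 + 0.494×0.506)/63] = 8.7 points. Stratified, using the average within-stratum variances: √[(0.2152 + 0.2412)/63] = 8.5 points.
- In 20,000 simulated trials the CI for the OR excluded 1 in 46.0% crude and 47.4% Mantel-Haenszel.
- With control rates of 42% and 34%, the crude OR is 1.99.

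**The case against.** The strongest reply is that the planned estimator is not worse for a descriptive purpose. Its RMSE around the within-stratum hazard ratio is lower in every row of the table, and its coverage is at least nominal. The extra intervals that exclude 1 are a gain in power, yet no decision rule uses this hazard ratio, and section 10.3.4 says no formal inference requiring a significance-level adjustment is planned. Marginal and within-stratum hazard and odds ratios differ by definition, so choosing between them is partly a choice of estimand. All of this stands, and it keeps the point small.

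The gain also depends on how prognostic prior TKI is, which the documents do not show. Under section 6.1, favourable-risk participants must have had sunitinib, a TKI, before randomisation to Track 1 nivolumab plus ipilimumab. That places better-risk control patients in the TKI-experienced stratum and could pull φ towards 1. The size of this effect is unknown.

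It can also be said that the wording about a single covariate does not literally rule out a strata term, that the SAP or a sub-protocol may add one, and that the study is closing with one patient in safety follow-up. The documents do not say whether any Track 1 arm reached the end of Stage 2. A stratified analysis is therefore not excluded, but it is not stated either. The late stage is a reason to keep the unstratified results alongside; it does not make the wording costly.

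**Conclusion.** The point holds as a minor, optional improvement. Track 1 is randomised by prior TKI, the specified Cox model does not use it, and the ORR contrasts name no strata. With balanced strata there is no bias at a hazard ratio of 1, and the unstratified estimates remain valid marginal summaries.

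Stratifying gives the within-stratum effect that the randomisation supports, and a CI that excludes 1 somewhat more often when an effect exists: between about 1 and 7 percentage points for φ from 1.5 to 2.5 at a hazard ratio of 0.60. It moves the hazard ratio by at most about 0.03, does not lower RMSE, and gains nothing if prior TKI is not prognostic. For ORR the change is smaller still. These sizes rest on 63 per arm, balanced strata and assumed stratum effects.

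**What to change.** In section 10.3.1 or the SAP:

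- Estimate the Track 1 PFS and OS hazard ratios with a Cox model stratified by prior TKI as recorded at randomisation.
- Give Cochran-Mantel-Haenszel estimates of the odds ratio and the ORR difference by prior TKI, with 95% CIs, and say that the hazard and odds ratios are within-stratum measures.
- Keep the unstratified estimates as sensitivity analyses.
- Name the data field that supplies the stratum. Section 5.1.3.1 says "investigative sites are required to determine if a participant has previously received anti-PD-1, anti-PD-L1, anti-CTLA-4, or TKI treatment" before screening and has treatment status entered in the enrolment system. The enrolment inputs in section 7.2 list "Anti-PD-1, anti-PD-L1, or anti-CTLA-4 treatment experience" but not prior TKI.

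The cost is SAP wording and a few lines of code, with no new data or participants. The change covers only the prior-TKI stratum; the different randomisation schedules and allocation ratios as arms open (section 7.2) are a separate matter.

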10.3.2 Safety Analyses

All safety analyses will be performed on the treated population.

Table 10.3.2-1: Safety Analyses

Endpoint	Statistical Analysis Methods
Incidence of AEs, SAEs, AEs leading to discontinuation and deaths. AEs will be graded according to CTCAE Version 4.03.	Frequency distribution of treated participants with AE using the worst CTC grade on treatment. Participants will be counted once at the PT level, once at the system organ class level, and once in the “Total subject” row at their worst CTC grade, regardless of SOC or PT.
Laboratory abnormalities Laboratory values will be graded according to CTCAE Version 4.03.	Laboratory shift table using the worst CTC grade on treatment per participant.

Abbreviations: AE = adverse event; CTC = common terminology criteria; PT = preferred term; SAE = serious adverse event; SOC = system organ class.

Same treatments under different Tracks with different populations may be combined for safety analyses.

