Oxygen Saturation	X	As clinically indicated			Record at rest and after mild to moderate exertion via pulse oximetry
Vital Signs and Weight	X	X	X		Includes body temperature, seated blood pressure, and heart rate.
Karnofsky Performance Status	X	X	X		
Review of Concomitant Medications	X	X	X		
Laboratory Tests					
Hematology and Serum Chemistry	X		X		
PK Samples ^c		X			Details are provided in each FRACTION-RCC Sub-Protocol
Anti-drug Antibody Samples ^c		X			Details are provided in each FRACTION-RCC Sub-Protocol
AE Reporting					
Monitor for Nonserious AEs	X	X	X		Nonserious AEs must be collected from first dose until 100 days following the last dose of study treatment. All SAEs and AEs will be assessed using NCI CTCAE Version 4.03.

Table 2-3: Follow-up Procedural Outline

Procedure	Safety Follow-up			Response/Survival Follow-up	Notes
	FU 1 30 Days ^a (± 7 Days)	FU 2 60 Days (± 7 Days)	FU 3 100 Days (± 7 Days)	Begins after Completion of Safety Follow-up Every 12 Weeks (± 2 Weeks) until 2 Years after Last Dose ^b	
Monitor for SAEs	X	X	X		All SAEs must be collected from the date of the participant's written consent until 100 days post discontinuation of dosing or participant's participation in the study if the last scheduled visit occurs at a later time. All SAEs and AEs will be assessed using NCI CTCAE Version 4.03.
Efficacy Assessments					
Tumor Response Assessment ^c	X		X		Assessed by RECIST v1.1 criteria (see Appendix 5). Participants with a history of brain metastasis should have an MRI (preferred) or CT of the brain if clinically indicated. Participants with a history of bone metastasis should have a bone scan if clinically indicated. All participants should receive scans at FU1, or 30 days (+ 7 days), except for participants with PD who started subsequent therapy or have already been treated beyond progression. Scans at FU3, or 100 days (+ 7 days), and every 12 weeks (+ 14 days) will only be collected for participants with CR, PR, or SD at treatment discontinuation.

Table 2-3: Follow-up Procedural Outline

Procedure	Safety Follow-up			Response/Survival Follow-up	Notes
	FU 1 30 Days ^a (± 7 Days)	FU 2 60 Days (± 7 Days)	FU 3 100 Days (± 7 Days)	Begins after Completion of Safety Follow-up Every 12 Weeks (± 2 Weeks) until 2 Years after Last Dose ^b	
Patient-reported Outcomes Assessment ^c	X	X	X		EQ-5D-3L and FKSI-DRS Can be collected over the phone at regularly scheduled time if needed.

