5 STUDY DESIGN

5.1 Overall Design

This is a rolling, Phase 2, adaptive study that will evaluate the preliminary efficacy, safety, tolerability, PK, and pharmacodynamics of novel FRACTION-RCC study treatment combinations in participants with advanced RCC. All novel treatment combinations will contain nivolumab. The details pertaining to the specific study treatment regimens are provided in each FRACTION-RCC Sub-Protocol.

Participants will be enrolled in 1 of 2 Tracks. Participants who are anti-PD-1, anti-PD-L1, and anti-CTLA-4 treatment naïve will be eligible for Track 1 and will be stratified by whether or not the participant has had prior TKI treatment. Participants who have had prior anti-PD-1, anti-PD-L1, or anti-CTLA-4 treatment will be assigned to Track 2, as outlined in [Figure 5.1-1](#) and described in [Section 5.1.1](#).

[figure not shown]
Participants on Tracks 1 and 2 will begin on the Treatment Phase (with a total duration of approximately 2 years). Tumor assessments will be conducted according to the timing described in each FRACTION-RCC Sub-Protocol.

Participants on Tracks 1 and 2 will be treated until completion of the Treatment Phase, progression, toxicity, or protocol-specified discontinuation (see [Section 8.1](#)). The decision to continue treatment beyond investigator-assessed progression is possible (for up to completion of that Treatment Phase) and should be discussed with the BMS Medical Monitor (or designee) and documented in the study records (see [Section 7.4.2](#)). In addition, a participant with progressive disease (PD) will have the option to enter into Track 2, assuming that he or she continues to fulfill all eligibility criteria at each new randomization point, including a life expectancy of ≥ 3 months (see [Section 5.1.1](#)). Re-randomization is no longer applicable per Protocol Amendment 07.

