Taken together, the data suggest a shorter duration of nivolumab of only 1 year was associated with increased risk of progression in previously treated patients with NSCLC, suggesting that treatment beyond 1 year is likely needed. Also, treatment beyond 2 years is unlikely to confer additional clinically meaningful benefit and that the risk of progression after discontinuing treatment at 2 years is low.

Collectively, these data suggest that there is minimal, if any, benefit derived from continuing IO treatment beyond 2 years in advanced tumors. However, even though immunotherapy is well tolerated, patients will be at risk for additional toxicity with longer term treatment. Therefore, in study CA018005, treatment with BMS-986217 and nivolumab will be extended for up to 2 years in this study.

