8.1.2 Study Treatment Combination Arm Discontinuation Criteria

In the event that 20% or more of study participants in a novel FRACTION-RCC study treatment combination arm of a given Track, at any given time, meet any of the toxicity criteria for permanent discontinuation (as described in [Section 8.1](#)), then consideration will be given to discontinue that FRACTION-RCC study treatment combination arm in that Track. This will include early side effects seen with combination agents and longer-term effects such as endocrinopathies. This action will be taken in consultation with the SMB and will consider other pertinent facts in coming to a

decision, including the toxicity profile of that combination seen outside FRACTION-RCC, participant benefit as measured by anti-tumor response, and comparison to nivolumab in combination with ipilimumab.

Discontinuation of a study treatment combination arm in a given Track for any reason WILL NOT lead to discontinuation for that combination in all Tracks. Safety of all open-label study treatment combination arms in other Tracks that contain the same agent (or agents) will be assessed by SMB and the Sponsor. In the event of serious, unexpected, or life-threatening emergent toxicities, relevant study treatment combination arms may then be modified to maintain the safety of participants. Decisions on such steps and the re-initiation of any study treatment combination arms that had been stopped would be made by SMB in consultation with the Sponsor and relevant authorities (eg, IRB/IEC).

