Section 2, Schedule of Activities; Table 2-2, Baseline for Re-randomization Procedural Outline; Section 3.1.1.2, Specific Attributes of the FRACTION Program Design; Section 5.1, Overall Design; Section 5.1.1, FRACTION-RCC Tracks 1 and 2 Design; Figure 5.1.1-1, Tracks 1 and 2 Study Design Schematic; Section 5.1.3.2, Treatment; Section 5.1.3.3, Follow-up; Section 5.4.1, Rationale for Duration of Therapy	Participants will receive treatment up to 2 years total duration.	Emerging data suggests that patients may derive clinical benefit beyond 6 months of immunotherapy. Therefore, patients will continue on study treatment for up to 2 years.
Table 2-1, Screening Procedural Outline	1. Duration of randomization prior to first dose extended	1. To allow patients to complete all the post randomization procedures required for a sub-protocol, duration between randomization and start of treatment can be extended from to allow for completion of study related tests.
	2. Data to be collected on toxicities from treatment with prior immunotherapies.	2. For patients previously treated with PD-1/PD-L1/CTLA-4, enrolling directly into Track 2, we will collect additional data on details of prior toxicities.
Table 2-3, Follow-up Procedural Outline	Karnofsky Performance Status assessment added at Follow-up visits 2 and 3	Collect performance status during follow-up.
Section 3.1, Introduction; Section 3.2.1, FRACTION-RCC	Included updates from recent clinical studies.	Most recent results of studies provided.
Throughout	Minor rewording/re-formatting for clarification.	Minor, therefore have not been summarized.

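### The master protocol summarises adverse events only as crude frequencies, although the collection window lengthens with time on drug; a time-at-risk rate and a Week 24 cumulative incidence should be added

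*Combined protocol and SAP*

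**What the plan says.** Section 4 makes safety a secondary objective, with incidence of AEs, SAEs, AEs leading to discontinuation, deaths and laboratory abnormalities as the endpoints. Section 10.3.2 gives the method:

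- Population: "All safety analyses will be performed on the treated population".
- AEs (Table 10.3.2-1): "Frequency distribution of treated participants with AE using the worst CTC grade on treatment". Laboratory values get a worst-grade shift table.
- Pooling: "Same treatments under different Tracks with different populations may be combined for safety analyses".

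The length of observation is set elsewhere:

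- Collection (Table 2-3): "Nonserious AEs must be collected from first dose until 100 days following the last dose of study treatment".
- Duration (Section 5.1): "Participants on Tracks 1 and 2 will be treated until completion of the Treatment Phase, progression, toxicity, or protocol-specified discontinuation". Section 5.4.1 puts the maximum at up to 2 years.
- Change over time (Appendix 9, Revised Protocol 04): "Therefore, patients will continue on study treatment for up to 2 years". The stated reason is benefit beyond 6 months of immunotherapy.

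Section 10.3 describes itself as a summary and defers to a statistical analysis plan to be finalised before database lock. Section 10 says that sub-protocols may add statistical considerations. Neither is among the documents in hand.

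**The concern.** A crude percentage combines how fast AEs occur with how long participants are watched. Here the second part depends on the arm's own performance, because treatment stops at progression and the AE window closes 100 days after the last dose. Treatment-naive and treatment-experienced Tracks can be expected to differ in time on drug, yet they may be pooled for safety. The plan handles efficacy differently: Section 10.3.1 uses Kaplan-Meier for the time-to-event endpoints and does not combine Tracks.

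The stake is interpretation. If one arm shows a higher AE percentage than nivolumab plus ipilimumab, Table 10.3.2-1 alone cannot show whether the regimen is more toxic per unit of time or simply kept participants on drug longer.

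**Working it through.** **The plan's own safety figure.** Section 10.1 gives 88% probability of seeing an AE of true rate 5% with 41 participants. Check: 1 − 0.95^41 = 87.8%, so it reproduces. The calculation treats the AE rate as one probability per person, with no time dimension.

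**Inputs for the illustration.** The documents give no AE hazard and no time on drug by arm, so these are assumptions:

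- Constant first-AE hazard of 20% by 24 weeks: λ = −ln(0.8)/24 = 0.00930 per week, the same in every arm and continuing through the 100 days off drug.
- Exponential time on drug with median m, so μ = ln 2/m, capped at 104 weeks.
- Medians of 3.7 and 5.5 months: treatment durations of everolimus and nivolumab in the phase 3 study described in Section 3.2.1. The 11.6 months is a median PFS for nivolumab plus ipilimumab from the other phase 3 study there, used as a proxy for a long time on drug.
- At 30.4375/7 weeks per month, the medians are 16.1, 23.9 and 50.4 weeks. The tail is 100/7 = 14.29 weeks.

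**Formulas.** On treatment: P = λ/(λ+μ) × [1 − exp(−(λ+μ) × 104)]. Treatment plus 100 days: 1 − (1 − P) × exp(−λ × 14.29), where the last factor is 0.8756.

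Worked for 5.5 months: μ = 0.02898, so λ/(λ+μ) = 0.2429 and exp(−3.981) = 0.0187. P = 0.2429 × 0.9813 = 23.8%. With the tail: 1 − 0.7617 × 0.8756 = 33.3%.

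| Assumed median on drug | On treatment only | Treatment + 100 days |
|---|---|---|
| 3.7 months | 17.7% | 27.9% |
| 5.5 months | 23.8% | 33.3% |
| 11.6 months | 36.7% | 44.6% |

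One hazard produces every row.

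**Does a rate remove the effect?** Only if person-time stops at the first event. In a separate simulation at one constant hazard (20% crude incidence at the 3.7-month median), time-at-risk rates were 2.71, 2.71 and 2.72 per 100 participant-months across the three medians. If first events are instead divided by the whole collection window, the hazard used in the table gives 39.1, 36.9 and 33.4 per 100 person-years, which reverses the distortion.

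**Is Week 24 a complete window?** No. Collection closes before Week 24 for anyone whose last dose falls before 24 − 14.29 = 9.71 weeks. Under the same model that is 1 − exp(−9.71μ) = 34%, 25% and 12.5% at the three medians, so a simple proportion by Week 24 would also be affected.

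**Early-onset AEs.** If the hazard is 0.10 per month for the first 3 months and zero afterwards, treatment plus 100 days covers the whole risk period. Incidence is then 1 − exp(−0.3) = 25.9% at every median. On treatment only it is 20.1%, 21.8% and 23.8%.

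**Protocol era.** The limit before Revised Protocol 04 is not stated. If it was 24 weeks, a 5.5-month median gives 25.2% over treatment plus 100 days, against 33.3% under a 104-week cap. The Synopsis also equates about 2 years of treatment with about 48 weeks; those figures must be reconciled.

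**The case against.** - **The gap may be filled elsewhere.** The SAP and sub-protocols are not in hand. A reader might infer that no time-adjusted AE analysis exists for this study. The documents support only that the master protocol does not specify one.
- **Crude incidence is legitimate.** It measures total burden, safety is descriptive here, and no between-arm safety test is planned. This stands, and is why the crude table should stay.
- **The effect depends on the AE.** It might be inferred that a longer-lasting arm must always show more AEs. The early-onset calculation shows otherwise.
- **The link to arm closure is inferred.** Section 8.1.2 lists among the facts to weigh "participant benefit as measured by anti-tumor response, and comparison to nivolumab in combination with ipilimumab". A reader might conclude that the crude percentages of Table 10.3.2-1 drive the decision to close an arm. The section does not say so. Its 20% trigger counts participants who meet toxicity criteria for permanent discontinuation, it prompts only consideration in consultation with the Safety Monitoring Board, and anti-tumor benefit is weighed alongside.
- **Era matters less than it seems.** Concurrently randomised arms share the same limit. Revised Protocol 04 therefore affects mainly non-concurrent comparisons and pooled tables, and the earlier limit of about 6 months is only implied.

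What remains is that, for AEs with a continuing hazard, the specified table cannot separate toxicity from duration, and unadjusted pooling across Tracks is allowed.

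**Conclusion.** The point holds as a limited, low-cost improvement to a descriptive secondary analysis. With a constant hazard, exponential time on drug and a 104-week cap, moving the median from 3.7 to 5.5 months raises crude incidence by 5.4 percentage points (27.9% to 33.3%). Moving it to 11.6 months raises it by 16.7 points (to 44.6%). These sizes rest on borrowed durations, one of them a PFS median, and on a hazard that persists off drug. For AEs confined to the first 3 months the effect is nil over the full window and small on treatment. The primary efficacy analysis is untouched. The documents do not support the stronger conclusions that safety reporting is necessarily biased against the more effective arm, or that an arm would be closed because of it.

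**What to change.** Keep the crude table as the measure of total burden. In Section 10.3.2, Table 10.3.2-1 and the SAP, add for any AE, grade 3-4 AE, SAE and AE leading to discontinuation, per arm and Track and before any pooling:

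1. The exposure-adjusted rate of first event per 100 person-years, with person-time from first dose to the earliest of first event, death, or 100 days after last dose.
2. The cumulative incidence of first event by Week 24, estimated by Aalen-Johansen with death as a competing event and censoring at the end of the AE collection window.

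Read both alongside the crude percentages when comparing with nivolumab plus ipilimumab or pooling Tracks. Compare with concurrently randomised controls, or show results by treatment-limit era. Define on treatment in Table 10.3.2-1 relative to the 100-day window. State when the window closes for re-randomised participants, whom Section 5.1.3.3 exempts from the three safety visits.

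Cost: SAP wording and a few tables from dates already collected, supplementary for any arm already locked. The rate in (1) assumes a roughly constant hazard, and (2) assumes that censoring at the end of AE collection is non-informative. Neither is sufficient alone, which is why both are proposed.
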